13.2 Statistical methods

Intention-to-treat (ITT) analysis will be performed as the primary analysis on all primary and secondary outcomes after the last participant has participated in the last visit. Missing values will be handled with a last observation carried forward approach for ITT analysis. Per-protocol (PP) analysis will only be performed in case of sensitivity testing.

Parametric tests (general linear models) will be used to test differences in outcomes from baseline to follow-up. Heterogeneity in responsiveness to the interventions will be tested by dividing each intervention group into smaller groups based on data distribution (medians) or clinically meaningful cut-points. If model assumptions cannot be met even after logarithmic transformation, non-parametric tests will be used. Plots of residuals versus predicted values will be used to judge normality. Metabolic patterns will be tested with multivariate statistics. Adjustment for relevant confounders will be performed. Two-sided tests will be used. *P* values of <0.05 are considered significant. The statistical programs SPSS and SAS will be used for data analysis.

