 - Carbohydrate intake (E%)
 - Total fat (E%)
 - Protein (E%)
 - Alcohol (E% and units/day) (women)
 - Alcohol (E% and units/day) (men)
 - Saturated fat (g/day) (women)
 - Saturated fat (g/day) (men)
 - Monounsaturated fat (g/day) (women)
 - Monounsaturated fat (g/day) (men)
 - Polyunsaturated fat (g/day) (women)
 - Polyunsaturated fat (g/day) (men)
 - Dietary fibre (g/day and g/10 MJ) (women)
 - Dietary fibre (g/day and g/10 MJ) (men)
 - Added sugar (g/day and g/10 MJ) (women)
 - Added sugar (g/day and g/10 MJ) (men)
- Self-reported physical activity (International Physical Activity Questionnaire – Short Form (IPAQ SF))
 - MET-minutes/week
 - Low, n and %
 - Moderate, n and %
 - High, n and %

Other outcomes

Number of visits with dietitians, endocrinologists, and diabetes nurses at V2 and V3 in each group.

Supplementary table with baseline characteristics for completers vs. non-completers with dropout before V2

- Number of participants, n
- Age (years)

- Gender, male, n and %
- Ethnicity, white, n and %
- Current smokers, n and %
- Self-reported educational level
 - Elementary school, n and %
 - Upper secondary education, n and %
 - Vocational, n and %
 - Short further (< 3 y), n and %
 - Medium further (3-4 y), n and %
 - Long further (> 4 y), n and %
 - Other education, n and %
- Living alone, n and %
- Body weight (kg), female
- Body weight (kg), male
- BMI, kg/m²
- Diabetes duration (years)
- HbA1c (mmol/l)

Analysis methods

Analyses of the primary outcomes will be performed based on efficacy estimates.

Adjustment for relevant confounders will be performed including adjustment for design variables used for stratified randomization based on the participants' gender, BMI and HbA1c at baseline.

Before further analysis and before unblinding, all variables will be inspected to detect outliers to uncover potential errors, such as registration errors.

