All continuous outcomes covered by this SAP will as a rule be modelled using baseline corrected repeated measures regression (20) with the following fixed effects and interactions between fixed effects: Visit, Visit (factorial)*Treatment. Data from V1, V2, and V3 will be included in the analysis. The models will be specified with a restricted maximum likelihood estimation method and a repeat on participant level (unstructured covariance structure). Model fit will be evaluated using graphical methods before estimating the treatment effects and if necessary, outcomes will be log-transformed. Estimated mean differences (CI95%) between groups (CI95%), conditional means (CI95%), and within group changes (CI95%) will be extracted from the model. For log-transformed outcomes the results will be back-transformed and be presented as the ratio between estimated mean differences (CI95%), estimated conditional geometric means (CI95%) and relative changes within groups (CI95%), respectively. If distribution assumptions cannot be met by log-transformation, a generalized mixed linear model with an appropriate distribution will be applied instead of the repeated measures regression model. In case the distribution does not comply with the distributions available in the generalized mixed linear model a non-parametric test will be used to compare the change scores for the given outcome.

Missing data

The number/frequency of missing values for the primary outcomes in each group at each time point will be provided. In the primary analysis, missing data are handled implicitly by maximum likelihood estimation in the linear mixed model and missing data will be assumed to be missing at random. This is equivalent to making multiple imputations for each treatment group separately and estimating the treatment effect that would have been found had all subject completed their assigned treatment (efficacy estimate) under the missing at random assumption.

Additional analyses

Not relevant.

Harms

Data on harms are not systematically collected and will not be reported.

Statistical software

SAS Enterprise Guide software version 8.3 or newer (SAS Institute Inc., Cary, NC, USA) and R software version 4.0.2 or newer (R Core Team, R Foundation for Statistical Computing, Vienna, Austria).

References

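### The SAP says its mixed model equals imputing each arm separately, but the model as written pools the baseline slope over the arms; the primary estimate is biased only if slopes differ by arm and drop-out also depends on baseline

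*SAP*

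**What the plan says.** Visit numbers here follow the SAP: V1 is baseline, V2 week 24 and V3 week 48.

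The SAP (Section 6, Analysis methods) models continuous outcomes with fixed effects "Visit, Visit (factorial)*Treatment", estimated by restricted maximum likelihood with "a repeat on participant level (unstructured covariance structure". It adds that "Data from V1, V2, and V3 will be included in the analysis". It does not say that the covariance is estimated by treatment group. The same section states: "Adjustment for relevant confounders will be performed including adjustment for design variables used for stratified randomization". No interaction of these variables with arm is given.

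Under Missing data, "missing data are handled implicitly by maximum likelihood estimation in the linear mixed model", and missing at random is assumed. The SAP then says: "This is equivalent to making multiple imputations for each treatment group separately". The Additional analyses entry is marked as not relevant, so no sensitivity analysis for missing data is planned.

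Protocol 13.2 says: "Heterogeneity in responsiveness to the interventions will be tested". Protocol 13.3 allows for drop-out of about 30%.

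**The concern.** Imputing each arm separately predicts a missing V2 value from that arm's own regression of V2 on V1, with its own slope and residual variance. A model with one covariance matrix for both arms has one slope and one residual variance. The SAP therefore claims a property that its stated model lacks.

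The property matters if the treatment effect changes with baseline. The arms then have different V2-on-V1 slopes, and a pooled slope is too flat for one arm and too steep for the other. If those who drop out also differ at baseline from those who stay, the two prediction errors need not cancel, and the treatment contrast is shifted although the data are missing at random.

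A modest shift could count in this trial. Under Objectives, the SAP requires both a confidence interval that excludes zero and a point estimate that reaches the minimal important difference: 3 mmol/mol for HbA1c or 0.3 mmol/l for MAGE. MAGE is measured only at V1 and V2, so a missing V2 value can be predicted from V1 alone.

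**Working it through.** **The plan's own figures.** The SAP attaches no number to the missing-data sentence. As background, Protocol 13.3 gives 87 per arm for a difference of 3.0, SD 7, 80% power and two-sided 5%. The normal formula gives 2 × (1.96 + 0.84)² × 7² / 3² ≈ 86; the t-based value is 86.4, rounded up to 87. So 87 is reproduced. The total of 226 is 174 × 1.30, which allows for a loss of 52/226 = 23%. I therefore use both 23% and 30% missing.

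**Step 1: what the stated model estimates.** With a common baseline mean, one covariance matrix and monotone drop-out, the V2 contrast equals the arm coefficient in a common-slope regression of V2 on V1 among those with V2 data. Direct maximum likelihood on one simulated two-visit trial (113 per arm, slopes 0.8 and 0.6, drop-out rising with baseline) gave −1.7745 by both routes. On the same data, arm-specific covariance gave −2.15 and separate-arm multiple imputation −2.12. The two approaches are not equivalent.

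**Step 2: large-sample bias.** Let b be the V2-on-V1 slope in each arm, b_p the pooled slope, and s the shift in mean baseline among those observed at V2. Then

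bias = (b_BCC − b_p) × s_BCC − (b_ctl − b_p) × s_ctl.

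If both arms have the same shift s, this reduces to (b_BCC − b_ctl) × s. It is zero if the slopes are equal, whatever the drop-out. It is also zero if drop-out is unrelated to baseline (s = 0).

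**Step 3: numbers.** None of these inputs is in the documents; they are assumptions: baseline HbA1c SD 10 mmol/mol, a logistic relation of drop-out to baseline (odds ratio per SD, same in both arms), and the slope gap (control minus BCC). Numerical integration gives s, and bias = gap × |s|, toward no effect:

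| Missing | Odds ratio per SD | s (mmol/mol) | Gap 0.1 | Gap 0.2 | Gap 0.3 |
|---|---|---|---|---|---|
| 30% | 1.5 | −1.18 | 0.12 | 0.24 | 0.35 |
| 30% | 2.0 | −1.90 | 0.19 | 0.38 | 0.57 |
| 30% | 2.2 | −2.11 | 0.21 | 0.42 | 0.63 |
| 23% | 1.5 | −0.91 | 0.09 | 0.18 | 0.27 |
| 23% | 2.2 | −1.64 | 0.16 | 0.33 | 0.49 |

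The bias scales with the assumed baseline SD: at SD 8, every entry is multiplied by 0.8.

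**Step 4: check at trial size.** I simulated 113 per arm, 30% missing, residual SD 6.5 and true effect −3.0, with 20,000 runs per scenario:

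| Slopes (control / BCC), odds ratio | Pooled: bias (SD) | By arm: bias (SD) | Estimate reaches 3.0: pooled v by arm |
|---|---|---|---|
| 0.70 / 0.60, 1.5 | +0.12 (1.03) | +0.01 (1.04) | 45% v 50% |
| 0.70 / 0.50, 2.2 | +0.42 (1.04) | 0.00 (1.07) | 35% v 50% |
| 0.75 / 0.45, 2.2 | +0.62 (1.07) | −0.01 (1.09) | 28% v 51% |
| 0.70 / 0.70, 2.2 | +0.01 (1.04) | 0.00 (1.07) | 50% v 50% |
| 0.75 / 0.45, 1.0 | −0.01 (1.07) | −0.01 (1.06) | 51% v 51% |

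**Step 5: cancellation and reversal.** With slopes 0.8 and 0.6 and 30% missing, an odds ratio of 2 in the BCC arm only gives about +0.18. Odds ratio 2 in one arm and 0.5 in the other gives about 0. Odds ratio 0.5 in both arms gives −0.38, which overstates the effect.

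**MAGE.** The same formula applies, in units of baseline SD: gap 0.2 and odds ratio 2 at 30% missing give 0.2 × 0.19 = 0.038 baseline SDs. The documents give no baseline SD for MAGE, so I do not convert this.

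**The case against.** The strongest reply is that a common covariance matrix is a usual mixed-model assumption, that the discrepancy is one inexact sentence, and that harm needs two further conditions for which the documents give no evidence. Much of this stands.

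- A reader might infer that the estimate is biased whenever response depends on baseline. It is not: dependence that is the same in both arms gives no bias.
- A reader might infer that the protocol expects BCC to work better at high HbA1c. It does not say so. Protocol 13.2 plans to test heterogeneity without naming baseline HbA1c, and the sub-hypotheses in 7.1 tie response to numeracy, estimation accuracy, consistency and adherence. Nothing says that participants with high HbA1c leave more often.
- The upper scenario is strong. A slope gap of 0.3 changes the treatment effect by 0.3 × (97 − 53) = 13.2 mmol/mol across the eligible HbA1c range. An odds ratio of 2.2 at 30% missing means drop-out of about 46% at +1 SD against 15% at −1 SD.
- The simulation uses two visits and leaves out the stratification adjusters; the planned HbA1c model has three visits. Under monotone drop-out V3 adds nothing about a missing V2 value, and adjusters without an arm interaction do not restore arm-specific slopes. For non-monotone gaps the sizes are only indicative.
- The single matrix is inferred because no grouping is stated. The sentence about separate groups might mean that grouping was intended; if so, the model specification needs to say it.

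None of this makes the equivalence true of the model as written, and no other planned analysis would show the difference.

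**Conclusion.** The equivalence sentence does not hold for the stated model. That part rests only on the plain reading of the SAP.

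The effect on the primary result is conditional. It needs slopes that differ by arm together with drop-out that depends on baseline, and it can cancel or reverse. Under the assumed inputs, with drop-out rising with baseline in both arms, the HbA1c effect is understated by about 0.1 to 0.6 mmol/mol, which is roughly a tenth to six tenths of the standard error. If the true effect is exactly 3.0, the chance that the point estimate reaches 3.0 falls from about 50% to between 45% and 28%.

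The documents do not support reading this as a failure of the missing-at-random analysis in general, or as a bias known to be present. It is a correctable mismatch with a modest possible effect on a decision rule that depends on the point estimate.

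**What to change.** For the two primary outcomes, HbA1c and MAGE, specify the unstructured covariance by treatment arm. Name the pooled-covariance fit as the fallback if the arm-specific fit does not converge. Reword the sentence to match: missing values are handled with arm-specific covariances under missing at random, with the baseline mean common to both arms. That last clause is needed because, with a shared baseline mean, even the arm-specific model is not exactly separate imputation.

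For secondary outcomes, especially those split by sex, either do the same where the model converges, or keep the common covariance, delete the claim about separate groups and state the common-covariance assumption. Arm-specific fits in the smaller sex-specific subsets were not tested here.

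The cost is one code option and one or two SAP sentences. A three-visit unstructured matrix has six parameters, so grouping by arm adds six; for MAGE, with two visits, it adds three. In the simulations the SD of the estimate rose by at most about 3%.

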9.1.2 Secondary outcomes

Changes in HbA1c from baseline to 6-months follow-up (week 48) between and within the two study groups (BCC and control).

Changes from baseline to the end of the intervention period (week 24) and at 6-month follow-up (week 48) between and within the two study groups (BCC and control) in:

- Body weight
- Blood pressure
- Lipid profile: low-density lipoprotein cholesterol (LDL-C), high-density lipoprotein cholesterol (HDL-C), total cholesterol (TC), free fatty acids (FFA) and triglycerides (TG)
- Waist and hip circumference
- Mathematical literacy
- Carbohydrate estimation accuracy
- Self-reported diet-related quality of life, perceived competencies in diabetes, health-care climate and physical activity

Changes from baseline to the end of the intervention (week 24) between and within study groups in:

- Other parameters of plasma glucose variability including time in range (3.9-10.0 mmol/l), % time spent in hypoglycaemia (<3.9 mmol/l), % time spent in hyperglycaemia (e.g. >11.1 mmol/l) and standard deviation of mean plasma glucose
- Body composition
- Dietary intake (total energy, intake of carbohydrate, fat, protein, added sugar and dietary fibre)

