10.2 Blood samples

Participants must attend V1, V5 and V6 after 8-10 hours of fasting having consumed only water for collection of blood samples. A small venous catheter will be inserted in one of the participant's arms for blood sampling which will be performed by a trained biomedical laboratory technician in the Clinical Biochemical Department at SDCC. The samples will be used for assessment of C-peptide, triglycerides, total cholesterol, HDL-C, LDL-C, very-low-density-lipoprotein cholesterol (VLDL-C), HbA1c, fasting glucose, haemoglobin, creatinine, albumin, potassium, sodium, alanine aminotransferase (ALAT), thyroid-stimulating hormone (TSH), leucocytes, thrombocytes, cobalamin and alkaline phosphatase according to standard procedure. No tobacco smoking is allowed in the morning before the visit. HbA1c will also be measured at the screening visit and visits V2, V3 and V4 in a non-fasting condition.

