10.6 Dietary assessment

Participants are asked to complete four days of weighed dietary food records after V1 and V5. Participants will receive oral and written instructions about how to record their food intake in the same four days as they collect their urine and while wearing a CGM, preferably on four consecutive days including three weekdays and one day in the weekend to capture a representative weekly diet for assessment of total energy and macronutrient intake. All food and beverages consumed during the three days of recording must be noted in a dietary registration form with as many details as possible which include recording of pre- and post-meal plasma glucose levels, physical activities and for insulin users - insulin type and dose taken are also recorded (appendix 6). The exact amount of the food should be determined preferably by weighing the food on a digital scale, but in situations where this is not possible (e.g. when dining out) the estimated portion size using household measurements or other well-defined units will be accepted. Participants are asked to hand in the dietary registration form at V2 for baseline measurements and by mail or in person after V5. Instructions will be giving by study personal with a nutritional background well trained in performing and assessing dietary food records. After receiving the dietary registration forms the records will be visually inspected immediately for clarification of possible misunderstandings. Subsequently, the nutrient intake based on the dietary records will be calculated using the software system Vitakost (Vitakost Aps, Kolding) where nutrient and energy calculations are based on the Danish national food database. The dietary food records are used to estimate total energy intake (kJ/d), total carbohydrate intake (g/day and g/meal) and total dietary fibre intake (g/d g/10 MJ).

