15.2 Ethical conduct of the study

The study will be conducted in accordance with the ethical principles in the Declaration of Helsinki and to the regulations for Good Clinical Practice (GCP) to the extent that this is relevant for a nonmedical study. The study will deliver important new knowledge on the effects of different dietitianled dietary interventions in patients with T2D in relation to glucose regulation and related metabolic parameters. In addition, the results from the study will give valuable information on patient self-care and adherence to their diabetes treatment through which the patients may experience reduced fluctuations in plasma glucose levels, including hypoglycaemia and increased diet-related quality of life. The findings from the study may have direct patient-related implications for future national guidelines and may potentially reduce the long-term diabetes-related complications.

This non-pharmacological study has no obvious ethical concerns for the participants and only minor risks in relation to participation (please see section 15.3). The anticipated benefits for the participants are high including improved glycaemic control in terms of reduced HbA1c and plasma glucose variability as well as an improvement of diet-related quality of life and self-care.

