15.3 Risks related to participation

Overall, limited risks are expected with the current study. All equipment used in the studies meet the requirements for patient safety and has previously been used in research projects without problems. There is a very small risk of hypoglycaemia at the study visits where participants must meet after an overnight fast of 8-10 hours for study measurements in a fasting state at three visits (V1, V5 and V6). In such cases the study investigator and study personnel will take appropriate action to protect participants.

Blood samples

Collection of data in the present study involves blood samples. A minor risk of slight pain during injection of the needle is present, and the sampling might leave a minor bruise at the place of injection. This will disappear within one to two days. Blood will be collected at four visits during the study period of 48 weeks corresponding to a total amount of 185 ml including 30 ml blood for a biobank for future research.

CGM

CGM will be used to measure the interstitial glucose at near continuous intervals to obtain a 24-hour glucose profile for a period of 6 days. The use of CGM involves insertion of a glucose sensor on the lower part of the abdomen (under the umbilicus) with an introducer needle to aid in the insertion of the sensor into the subcutaneous tissue. There is a minor risk of slight pain during injection of the needle. Also, a minor risk of skin irritation or infection due to either the sensor needle or the adhesive can occur.

DXA

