15.5 Protocol changes

Substantial amendments to this protocol may be implemented only after a favourable opinion of the Ethics Committee of the Capital Region, Copenhagen has been obtained. Amendments to the protocol are regarded as substantial if they have a significant impact on

- The safety, physical health and mental integrity of the participants
- The scientific value of the study
- The conduct or the management of the study

Any amendments to this protocol will be signed by the signatories included in section 2. If an event occurs related to the conduct of the study which may affect the safety of the participants, the study investigator may take appropriate measures to protect the participants against immediate hazards. The investigator will inform Ethics Committee of the Capital Region, Copenhagen of the new events and the measures taken as soon as possible.

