Estimation of minimal important difference for primary outcome: Reductions in HbA1c of 3 mmol/mol and 0.3 mmol/l of MAGE were defined as minimal important differences in this trial. This was primarily based on findings from clinical trials of different dietary approaches for reducing HbA1c in T2D (18, 19). Since no studies had examined the effect of dietary interventions using MAGE as an outcome in our target population with T2D at the time. Thus, based on previous findings (18, 19) we expected to find HbA1c reductions around 3 mmol/mol compared to standard care. This was considered clinically relevant as part of a multidisciplinary approach for the management of hyperglycaemia in T2D.

Secondary/descriptive/exploratory outcomes

The treatment effect will be given as the baseline corrected difference between the groups at V2 and V3. No minimal clinically relevant differences were defined for these outcomes.

- HbA1c (mmol/mol) (only for V3)
- Total body weight (kg), women
- Total body weight (kg), men
- BMI (kg/m²)
- Blood pressure
 - Systolic blood pressure (mmHg)
 - Diastolic blood pressure (mmHg)
- Fasting concentration of plasma lipids
 - Total cholesterol (mmol/l)
 - LDL cholesterol (mmol/l)
 - HDL cholesterol (mmol/l)
- Anthropometry
 - Waist circumference, cm (women)
 - Waist circumference, cm (men)
 - Waist/Hip ratio, unitless (women)
 - Waist/Hip ratio, unitless (men)
- Blinded CGM data (not measured at V3)
 - Mean plasma glucose, mmol/l
 - Time in range (TIR): % of readings and time 3.9-10.0 mmol/l
 - Time above range (TAR): % and readings and time 10.1-13.9 mmol/l
 - Time below range (TBR): % readings and time 3.0-3.8 mmol/l
 - Glycaemic variability, coefficient of variation (CV), %
 - Glycaemic variability, standard deviation (SD), mmol/l
- Numeracy skills test

- Total score
- Correct answers, n and %
- Carbohydrate estimation accuracy test based on 11 high-carb foods (only for foods reported eaten)
 - Estimation errors in %
- Self-reported diabetes diet-related quality of life (DDRQOL), total score within each subscale
 - General perception of diet
 - Satisfaction with diet
 - Restriction of social functions
 - Burden of dietary therapy
 - Perceived benefits of dietary therapy
 - Mental health
 - Vitality
- Self-reported Perceived Health Competence Scale (PCS), total score
- Self-reported Healthcare Climate Questionnaire (HCCQ) (not measured at V3), total score
- Dietary intake (not measured at V3)
 - Total energy intake (kJ/day)

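### The SAP declines to report harms, and its only time-below-range measure omits glucose below 3.0 mmol/l, although the protocol collects relevant data in both arms

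*SAP*

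**What the plan says.** SAP Section 6, Harms, consists of one sentence: "Data on harms are not systematically collected and will not be reported".

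The protocol schedules the following for all participants:

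- **Glucose.** Section 10.4 provides six days of CGM after V1 and again after V5. Section 9.1.2 names, as a secondary outcome to week 24, the percentage of "time spent in hypoglycaemia (<3.9 mmol/l").
- **Blood tests.** Section 10.2 lists a fasting panel that includes haemoglobin, creatinine, albumin, "potassium, sodium, alanine aminotransferase (ALAT), thyroid-stimulating hormone (TSH), leucocytes, thrombocytes, cobalamin and alkaline phosphatase according to standard procedure". Table 4 marks these at V1, V5 and V6.
- **Withdrawals.** Section 9.5.3 makes pregnancy and other safety concerns grounds for withdrawal and asks for the reason to be documented.
- **Notification.** Section 15.5 covers events in the conduct of the study that may affect participants' safety: "The investigator will inform Ethics Committee of the Capital Region, Copenhagen of the new events and the measures taken as soon as possible".

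The corresponding SAP outcome is "Time below range (TBR): % readings and time 3.0-3.8 mmol/l". The SAP numbers its visits differently: protocol V1, V5 and V6 (baseline, week 24, week 48) are SAP V1, V2 and V3.

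**The concern.** Hypoglycaemia matters in this trial. Protocol 9.5.1 admits patients on any glucose-lowering medication, and the SAP baseline table has rows for basal, prandial and mixed insulin and for SU. The protocol background (6.1) suggests that greater awareness may lower carbohydrate intake. Section 15.2 presents "reduced fluctuations in plasma glucose levels, including hypoglycaemia and increased diet-related quality of life" as something patients may gain. Section 15.3 acknowledges a risk, though only around fasting visits: "There is a very small risk of hypoglycaemia at the study visits where participants must meet after an overnight fast of 8-10 hours".

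A trial that puts forward less hypoglycaemia as a possible benefit should be able to show the opposite result if it occurs. If HbA1c falls in the BCC arm, readers will ask whether low glucose increased, and how low it went. A statement that harms will not be reported, together with a hypoglycaemia measure that stops at 3.0 mmol/l, leaves the second question unanswered although the sensors recorded the data.

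**Working it through.** The point rests on comparing the two documents. No sample-size or power figure is involved.

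**1. Hypoglycaemia definition.** Assume glucose is recorded to one decimal, so that the two definitions differ only in readings below 3.0 mmol/l. For one participant, let *a* be the share of CGM time at 3.0-3.8 mmol/l and *b* the share below 3.0 mmol/l.

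- Protocol outcome = *a* + *b*
- SAP outcome = *a*

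Two kinds of worsening can then be traced:

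| Change from baseline to week 24 | Protocol outcome | SAP outcome |
|---|---|---|
| Share *d* moves from 3.0-3.8 to below 3.0 | 0 | -*d* (looks better) |
| Share *e* moves from in range to below 3.0 | +*e* | 0 (not seen) |

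A reading that drops from 3.2 to 2.8 mmol/l is an example of the first row. Only the first row makes the SAP measure move the wrong way, and there the protocol's own measure stays flat. This is why the time below 3.0 mmol/l should be shown separately as well as within the total.

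**2. Laboratory results.** Table 4 lists 19 blood analytes. Four are post-baseline outcomes in the SAP: HbA1c and total, LDL and HDL cholesterol. That leaves 19 - 4 = 15. Of these, C-peptide, glucose, triglycerides and VLDL cholesterol are metabolic measures. The other 15 - 4 = 11 are haemoglobin, leucocytes, thrombocytes, creatinine, albumin, potassium, sodium, ALAT, alkaline phosphatase, TSH and cobalamin. None of the 11 appears in the SAP's baseline table or its outcome list.

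**3. Coverage of the glucose data.** Table 1 places V1 at weeks -4 to -1, so the first CGM window precedes the intervention and cannot show a treatment effect. Post-baseline CGM is the single window after V5:

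- Study length: 48 weeks x 7 = 336 days
- Post-baseline CGM: 6 / 336 = 1.8%

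There is no CGM at week 48.

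**4. Adverse events.** Neither Table 1 nor the visit descriptions in protocol section 11 include an adverse-event or hypoglycaemia question. The first half of the SAP's Harms sentence is therefore correct for events as such. The second half, that nothing will be reported, is what conflicts with items 1 and 2.

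**The case against.** The strongest reply is that the SAP already reports several outcomes on which harm could appear. It compares time at 3.0-3.8 mmol/l between groups at week 24. It compares every diet-related quality-of-life subscale, including the burden of dietary therapy, and protocol 7.1 itself predicts that this quality of life may fall with BCC. SAP Section 5 reports losses and exclusions by group with reasons. All of this stands. A reader might infer that the trial will show no harm side, or can say nothing about hypoglycaemia. The documents do not support that. SD and CV of glucose may also register deeper lows, but they cannot separate lows from highs.

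A second reply is that the blood tests are routine samples. That also stands in part: the protocol gives them no stated safety purpose, and 9.1.2 does not name the 11 tests as outcomes. The case for tabulating them is that they are collected in both arms on a fixed schedule, not that the protocol promised a safety analysis.

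Third, section 15.5 sits under protocol changes and its duty is conditional. It should not be read as a promise to collect events at visits.

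A reader might also want finger-stick values and a count of hypoglycaemic episodes. Protocol 10.6 does ask for "recording of pre- and post-meal plasma glucose levels, physical activities and for insulin users - insulin type and dose taken are also recorded", and 10.4 asks for four glucometer readings a day during CGM. However, neither document defines an episode; the 3.9 mmol/l limit is attached to percentage of time. Protocol 14.2 says in general terms that all sources are registered, but it names CGM and dietary data without naming finger-stick values. CGM is the firmer source.

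**Conclusion.** The point holds as a partial gap in reporting. The Harms sentence is right that adverse events and hypoglycaemic episodes are not systematically collected. Its refusal to report is inconsistent with the protocol's scheduled data and with the SAP's own time-below-range outcome. The most serious consequence is that all glucose below 3.0 mmol/l is left out of the SAP's categories, so worse hypoglycaemia could go unseen or register as improvement. The lesser one is that 11 blood tests at three visits have no reporting plan.

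How often readings below 3.0 mmol/l will occur cannot be judged from the documents, so the numerical effect on the result is unknown. The conclusion assumes that the SAP's 3.0-3.8 mmol/l band is meant literally and that the downloaded CGM data retain lower readings. The primary analysis and the sample size are unaffected.

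**What to change.** Replace the Harms sentence with a descriptive table by arm, drawn from data already collected:

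1. CGM percentage of time below 3.9 mmol/l in full, with the part below 3.0 mmol/l shown separately, and the number of participants with any such reading. Give this at baseline and week 24 (protocol V1 and V5; SAP V1 and V2), overall and by baseline insulin or SU use, with the number who had usable CGM as denominator.
2. The scheduled laboratory values at baseline, week 24 and week 48.
3. Withdrawals for safety reasons or pregnancy, and any events notified under protocol 15.5. The withdrawals largely restate reasons that the flow diagram will already give.

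Report as a limitation that adverse events were not elicited and that post-baseline CGM covers one six-day window, so an absence of reports is not evidence of no harm. Adding a question at visits is probably moot, because the SAP describes trial conduct in the past tense. If analysis has already begun, label the table as a later addition.

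The cost is SAP wording, some data cleaning, one or two extra tables and possibly a less favourable-looking report. No hypothesis test is added, so the false discovery rate procedure for secondary outcomes does not change.
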